##### *Distance VA*

Measure distance visual acuity using the 100% contrast ETDRS chart under photopic lighting at a distance of 4-6 m.

##### *Intermediate VA*

Have the subject hold a Logarithmic ETDRS Visual Acuity Chart, “Chart 2”, at 60cm, using the 60cm cord held at the outer canthus as a reference. Record and score the subject’s visual acuity.

##### *Near VA*

Conduct near testing with a Logarithmic ETDRS Visual Acuity Chart, “Chart 1” at 40 cm, using the 40cm cord held at the outer canthus as a reference. Visual acuity determined with the chart will be recorded and scored.

##### **9.4.4. Quality of vision questionnaire**

Have the subject complete the Q of V (Quality of Vision) questionnaire. Scoring will be through the aggregate spreadsheet provided.

Note: Avoid interpreting survey questions for subjects. That is, avoid re-phrasing questions if a subject asks, "What does this mean?"

#### **9.4.5. Binocular Defocus Curve**

With and without the manifest distance refraction in place in a phoropter, and in photopic conditions, perform binocular defocus curve testing. An over-correction starting at +1.0D is placed in the phoropter and binocular VA is recorded. The correction is then reduced by 0.5D (i.e. +0.5 over-correction) and retested. An over-correction of -4.0D is then placed in the phoropter and removed in 0.5D increments, testing VA at each step. The procedure ends with VA testing with a 0.0D over-correction (best-corrected distance refraction). Testing may be conducted using proprietary computer software designed to simplify the procedure and to record results. LogMAR visual acuity will be recorded for each defocus step.

### ***9.5. Unscheduled Visits***

Unscheduled exams may be conducted at the discretion of the Investigator with all relevant information from the exam recorded in the source documents and on the Unscheduled Visit pages within the CRF booklet.

### ***9.6. Discontinued Subjects***

Discontinued subjects are those who do not have an exit visit or who come into the office to be exited prior to the scheduled final study visit. Subjects may be discontinued from the study at any time if, in the opinion of the investigator, their continued participation in the study poses a risk to their health. The reasons for discontinuation include:

- a. Adverse event;
- b. Lost to follow-up;
- c. Subject decision unrelated to an adverse event;
- d. Protocol violation;
- e. Treatment failure;
- f. Other.

To ensure the safety of all subjects who discontinue prior to Visit 6, investigators should assess each subject and, if necessary, advise them of any therapies and/or medical procedures that might be needed to maintain their health. Any changes in medical health and/or use of concomitant medications should also be captured.

## **10. ANALYSIS PLAN**

### ***10.1. Analysis Data Sets***

All subjects who are enrolled in the study will be evaluated for safety. Efficacy analyses will be performed based on data from those eyes where uncomplicated Verion-LenSx guided arcuate incisions were completed.

### **10.2. Statistical Methodology**

All data will be collected by the site and entered into a spreadsheet. Subjects will be assigned an ID number. Data analysis will be performed without patient identification. Statistical analysis will be performed using standard descriptive statistics and other tests as deemed appropriate based on the characteristics of the data to be analyzed. All statistical tests will be two-sided and interpreted at a 5% significance level.

### **10.3. General Statistical Considerations**

The statistical analyses will be performed using Statistica, version 12 or higher. Any statistical tests of hypotheses will employ a level of significance of alpha=0.05.

## **11. SAMPLE SIZE JUSTIFICATION**

Data in the literature suggests that the ReSTOR non-toric IOLs (+3.0D and +2.5D) implanted in a group of eligible eyes showed a residual refractive cylinder of  $0.40D \pm 0.32D$ . (Gundersen KG, Potvin R. Comparison of visual outcomes and subjective visual quality after bilateral implantation of a diffractive trifocal intraocular lens and blended implantation of apodized diffractive bifocal intraocular lenses. Clin Ophthalmol. 2016 May 10;10:805-11). We are looking for the toric IOLs to be non-inferior. We powered the study using that mean and SD, a power of 0.9, an alpha of 0.05, and a 0.25D non-inferiority margin. The mean residual refractive cylinders will be compared using a t-test between the two groups, with the mean and SD from the literature (blended bifocal group) and the mean and SD from the current study. The required sample size is 29 subjects. Allowing for 10% dropout we will plan to enroll 32 subjects.

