### 3. GENERAL INFORMATION

Objective	To quantify and provide a normative standard for refractive and visual outcomes in eyes with significant corneal astigmatism undergoing cataract surgery with the Alcon Toric ReSTOR lens. As well as to quantify the postoperative rotational stability of the IOL.
	The hypothesis is that the addition of toricity will not affect the general performance of the ReSTOR design. As such, it is expected that patients with a ReSTOR toric IOL that achieve a correction of their astigmatism will have visual acuity and visual quality similar to patients implanted with the non-toric ReSTOR models. The Toric ReSTOR lenses (+2.5 and +3.0) will result in a residual refractive cylinder similar to that observed in patients with non-clinically significant astigmatism treated with non-toric ReSTOR lenses. They will also provide excellent distance and near vision in the vast majority of patients; we expect 75% of patients will have 20/25 (0.1 logMAR) or better uncorrected visual acuity at distance and near. The Toric-ReSTOR lens will demonstrate rotational stability that meets or exceeds the recommendations established by the American National Standards Institute.
Test Article(s)	Alcon Toric-ReSTOR +2.5 and +3.0 models
Control Article(s)	None.
Sample size	64 eyes of 32 subjects at 1 clinical site
Study Population	Subjects $\geq$ 30 years of age presenting for cataract surgery or refractive lens exchange surgery who are interested in astigmatism reduction and presbyopia correction. Subjects must be eligible for bilateral multifocal toric lens implantation.
Number of sites	One
Study Design	Prospective, non-randomized, single-arm, single center, open-label study.
Masking	None

Variables

Primary:

- Residual refractive cylinder

Secondary:

- Monocular and binocular Uncorrected and Best-corrected distance, intermediate (60cm) and near (40cm) visual acuity
- Postoperative orientation changes with the Toric ReSTOR IOL up to 3 months after surgery.
- Binocular Uncorrected and Best-corrected defocus curve (3 month visit).
- Quality of vision, measured with a subjective questionnaire.

Duration / Follow-up    Preoperative to 3 months postoperative

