## 7. SUBJECTS

### 7.1. *Subject Population*

Eligible test subjects will be patients presenting for cataract surgery or refractive lens exchange surgery who are interested in astigmatism reduction and presbyopia correction. Subjects must be eligible for bilateral multifocal toric lens implantation.

A total of 32 subjects at one site will be enrolled. Both eyes of a subject will be enrolled. Subjects must meet the inclusion criteria. Prior to enrollment, subjects will be provided information on the study and asked to sign a patient information and consent form to participate. The patient information and consent form will be approved by an appropriate ethics committee.

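### The 29 subjects for 90% power fit a one-sided 5% test with equal groups, not the two-sided 5% rule in section 10.2; actual power depends on an unstated comparator size and unit of analysis

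*Combined protocol and SAP*

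**What the plan says.** - **Section 11** takes a published value for the non-toric lenses, described as lenses "implanted in a group of eligible eyes showed a residual refractive cylinder of" 0.40 D with SD 0.32 D. It states a non-inferiority aim and sizes the study with "a power of 0.9, an alpha of 0.05, and a 0.25D non-inferiority margin". The test is a two-group t-test "with the mean and SD from the literature (blended bifocal group) and the mean and SD from the current study". The result: "The required sample size is 29 subjects", raised to 32 for 10% dropout.
- **Section 10.2**: "All statistical tests will be two-sided and interpreted at a 5% significance level".
- **Section 10.3**: "Any statistical tests of hypotheses will employ a level of significance of alpha=0.05", again without sidedness.
- **Unit.** Section 3 plans "64 eyes of 32 subjects at 1 clinical site" and section 7.1 says "Both eyes of a subject will be enrolled". Section 10.1 defines the efficacy data set by eyes, while section 11 counts subjects.

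The plan does not give the size of the published group, does not say how a subject's two eyes enter the primary test, and does not say which confidence limit at which level decides non-inferiority.

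**The concern.** A non-inferiority conclusion uses only one tail. A two-sided 5% test, read as a 95% confidence interval, spends 2.5% in that tail; a one-sided 5% test, read as a 90% interval, spends 5%. Section 11 does not say which it used, and no section exempts the primary test from section 10.2. If the 29 came from the one-sided 5% version, the 90% power belongs to a test other than the one section 10.2 prescribes.

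Two things are at stake. First, the power figure is the only justification for the sample size. Secondly, the error rate of the primary conclusion is left open: in an open-label study, the choice between a 90% and a 95% interval could be made after the data are seen. A two-sample t-test also cannot be run or powered without the size of the second group, and counting eyes instead of subjects changes the amount of information.

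**Working it through.** **Inputs from section 11:** SD σ = 0.32 D in both groups, margin Δ = 0.25 D, literature mean 0.40 D, target power 0.90, and true difference 0 (the plan powers on the same mean and SD for both groups). **Assumed, because the documents do not give them:** comparator size n₂ and between-eye correlation ρ.

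**Formula.** Power = P(T > t₁₋α, df), where T is noncentral t with df = n₁ + n₂ − 2 and noncentrality δ = Δ / [σ√(1/n₁ + 1/n₂)]. Here α is the one-tail level: 0.05 for one-sided 5%, 0.025 for two-sided 5%.

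**1. Reproducing 29.** With n₁ = n₂ = 29, σ√(2/29) = 0.0840 and δ = 0.25/0.0840 = 2.97, with df = 56.

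| Per group | One-sided 5% | Two-sided 5% (2.5% in one tail) |
|---|---|---|
| 28 | 0.893 | 0.819 |
| **29** | **0.902** | **0.832** |
| 35 | 0.944 | 0.896 |
| 36 | 0.949 | 0.905 |

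So 29 is the minimum under one-sided 5%, and 36 is the minimum under section 10.2's rule. The normal approximation n = 2σ²(z₁₋α + z₀.₉₀)²/Δ² agrees: 28.06, rounded up to 29, and 34.4, rounded up to 35. Other readings do not give 29. A one-sample test against a fixed reference needs 16 (one-sided 5%) or 20 (two-sided 5%). Taking 29 as the total of both groups gives power of only 0.66, even at one-sided 5%.

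**2. Dependence on comparator size,** with 29 toric units:

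| Assumed n₂ | One-sided 5% | Two-sided 5% |
|---|---|---|
| 15 | 0.780 | 0.670 |
| 20 | 0.842 | 0.749 |
| 29 | 0.902 | 0.832 |
| 40 | 0.936 | 0.884 |
| 46 | 0.947 | 0.902 |
| 60 | 0.963 | 0.927 |

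Reaching 90% takes at least 29 comparator units under one-sided 5% and at least 46 under two-sided 5% (45 gives 0.899). If all 32 subjects complete and n₂ = 32, two-sided power is 0.868.

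**3. Dependence on the unit.** If both eyes of 29 subjects are analysed, the effective size is 58/(1 + ρ). Against 29 independent comparator units, two-sided rule:

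| Assumed ρ | Effective n₁ | Power |
|---|---|---|
| 0 | 58 | 0.925 |
| 0.25 | 46.4 | 0.903 |
| 0.5 | 38.7 | 0.880 |
| 0.75 | 33.1 | 0.856 |
| 1 | 29 | 0.832 |

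**4. Where the two rules disagree.** At 29 versus 29 with both SDs 0.32 D, the largest observed toric mean that passes is 0.40 + 0.25 − t × 0.0840:
- 90% interval: t = 1.673, giving 0.509 D.
- 95% interval: t = 2.003, giving 0.482 D.

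The rules differ only for an observed mean between about 0.48 and 0.51 D. At zero true difference that is about 7% of outcomes (0.902 − 0.832).

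**The case against.** The best counter-argument is that no shortfall has been shown. The published group is identified, its size may be retrievable from the cited paper, and 46 or more comparable units would give 90% power even under the two-sided rule. That stands, and the conclusion is conditional for this reason.

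A second argument is that the published mean is already fixed at 0.40 D. If only the toric sample varies and the true toric mean equals that value, simulating the same two-sample rule at two-sided 5% gives about 91% at a comparator of 29, with 90% reached at about 27. This is a legitimate reading, but it is not how 29 was obtained: 29 comes from conventional two-sample power, in which both means vary. The 83% is the like-for-like figure and should be read with that condition.

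Thirdly, section 10.2 can be read as already settling sidedness for sections 10.3 and 11. If so, the test rule is clear, but the sample size was then computed for a different rule.

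Finally, the practical effect is modest: the two rules disagree only over a narrow band of observed means, in a single-arm study with largely descriptive aims. This limits the weight of the point but does not reconcile the two sections. Section 10.1's reference to eyes does not settle the unit either, because section 11 counts subjects.

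**Conclusion.** The point holds. No calculation in section 11 is wrong in itself: 29 is correct for a one-sided 5% test with equal groups. But 90% power does not follow from the two-sided 5% rule in section 10.2. On the plan's own equal-group basis, power under that rule is 83%, and 36 per group would be needed for 90%.

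The actual power cannot be stated from the documents. It could be well below 90% with a small published group or above it with a larger one, and it also shifts with the handling of two eyes per subject. These figures assume a common SD of 0.32 D, zero true difference and a published mean carrying its own sampling error; comparator sizes and between-eye correlations are assumed values. The point should be fixed, because it concerns the primary comparison and the only basis given for the sample size.

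**What to change.** Reconcile sections 10.2 and 11 before the data are analysed:

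1. **Decision rule.** For example: *Non-inferiority is concluded if the upper limit of the two-sided 95% confidence interval for the toric mean minus the literature mean of residual refractive cylinder is below 0.25 D.* Alternatively, declare the primary test one-sided at 5% (90% interval) as an explicit exception to section 10.2.
2. **Unit of analysis.** Either the eye, with an adjustment for two eyes per subject, or the subject, stating how the eyes are combined. Align sections 10.1 and 11.
3. **Comparator.** Give the published group's size in a compatible unit.
4. **Power.** Restate it for the chosen rule, unit and comparator size, and say whether the published mean is treated as fixed or as estimated.

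The cost is wording in sections 10.1, 10.2 and 11 and one recalculated power figure, which may be less favourable than 90%. No added patients are needed to make the correction.

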### ***7.3. Exclusion Criteria***

If any of the following exclusion criteria are applicable to the subject or either eye, the subject should not be enrolled in the study.

- Irregular astigmatism (e.g. keratoconus)
- Corneal pathology (e.g. opacities, EBMD, Fuch's dystrophy, etc.)
- Monocular status (e.g. amblyopia)
- Previous radial keratotomy, corneal refractive surgery or other corneal surgery (e.g. corneal transplant, DSAEK, lamellar keratoplasty)
- Previous anterior or posterior chamber surgery (e.g., vitrectomy, laser iridotomy)
- Moderate-to-advanced glaucoma
- Strabismus
- Use of arcuate incisions for astigmatism management at the time of surgery
- Diabetic retinopathy
- Macular pathology (e.g. ARMD, ERM, etc.)
- History of retinal detachment

- Subjects who have an acute or chronic disease or illness that would confound the results of this investigation (e.g., immunocompromised, connective tissue disease, clinically significant atopic disease, diabetes, and any other such disease or illness), that are known to affect postoperative visual acuity.
- Participation in (or current participation) any investigational drug or device trial within the previous 30 days prior to the start date of this trial.

The principal investigator reserves the right to declare a patient ineligible or non-evaluable based on medical evidence that indicates they are unsuitable for the trial.

Pregnancy has a known effect on the stability of refractions and visual acuity. As such, subjects who become pregnant during the study will not be discontinued but their data may be excluded from analyses of effectiveness.

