## 15. STANDARD EVALUATION PROCEDURES

**Table 15.1. Proposed Visits and Study Assessments**

(visits are by patient, with both eyes tested)

Activity	Pre-operative	Operative	Postoperative			
	Visit 1	Visit 2, 2A	Visit 3, 3A	Visit 4, 4A	Visit 5	Visit 6
			1 Day	1 Week	1 Month	3 Month
Informed Consent	X					
Demographics	X					
General Information: Medical History	X					
Surgery		X				
Manifest Refraction	X				X	X
Uncorrected Distance VA (monocular and binocular)			X	X	X	X
Corrected Distance VA (monocular and binocular)	X				X	X
Uncorrected Intermediate and Near VA (monocular and binocular)					X	X
Distance-corrected Intermediate and Near VA (monocular and binocular)					X	X
Intraocular pressure			X	X	X	X
Verion photograph	X	X			X	X
Quality of vision questionnaire						X
Binocular Defocus curve (uncorrected and corrected)						X
Monitor for Adverse Events		X	X	X	X	X
Complete Exit Form 						X

 Complete Exit Form upon termination of subject participation, or at Visit 6, whichever occurs first.

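### The t-test for residual cylinder does not state its unit or allow for two eyes per subject; if eyes enter as independent values, its standard error is too small

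*Combined protocol and SAP*

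**What the plan says.** Section 11 sets a non-inferiority comparison of residual refractive cylinder with a margin of 0.25 D: "The mean residual refractive cylinders will be compared using a t-test between the two groups". One group is represented by a published mean and SD (0.40 D, SD 0.32 D), the other by the mean and SD of this study. The section does not say whether an observation is an eye or a subject, and it gives no number of units for the literature group.

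The indications of the unit point in different directions:

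- Subjects: "The required sample size is 29 subjects" (section 11).
- Eyes, for the cited figure: the non-toric lenses "implanted in a group of eligible eyes showed a residual refractive cylinder of" 0.40 D (section 11).
- Both: "64 eyes of 32 subjects at 1 clinical site" (section 3); "Both eyes of a subject will be enrolled" (section 7.1); "visits are by patient, with both eyes tested" (Table 15.1).
- Eyes, for the efficacy set: "Efficacy analyses will be performed based on data from those eyes where uncomplicated Verion-LenSx guided arcuate incisions were completed" (section 10.1). This is weak evidence, because section 7.3 lists as an exclusion "Use of arcuate incisions for astigmatism management at the time of surgery".

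Sections 10.2 and 10.3 add descriptive statistics, unspecified further tests suited to the data, a two-sided 5% level and the software. No two-eye average, single-eye rule, mixed model, GEE or cluster-robust standard error appears anywhere.

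**The concern.** A subject's two eyes usually resemble each other, so two eyes carry less information than two independent observations. A plain t-test on all eyes ignores this. For any positive correlation it gives too small a standard error for the toric mean, and it declares non-inferiority too easily when the true difference is near the margin.

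The study aims to provide a normative standard (sections 3 and 6), so the precision attached to the mean matters in its own right. With the unit open, the same data give standard errors of different size, and the choice could be made after the data are seen.

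**Working it through.** **Inputs from the plan.** SD 0.32 D, margin 0.25 D, power 0.9, alpha 0.05 and 29 subjects (section 11); two eyes per subject (section 7.1), so 29 × 2 = 58 evaluable eyes; two-sided 5% tests (section 10.2), which is 2.5% on the non-inferiority side.

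**Assumptions.** The documents give no between-eye correlation ρ, so 0.3/0.5/0.7 is used throughout. They give no literature sample size m, so 29 to 100 independent units is used. The 0.32 D is taken as a per-eye SD.

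**1. The plan's own figure.** n per group = 2 × [0.32 × (1.645 + 1.282) / 0.25]² = 28.1, rounded up to 29. A noncentral-t check also gives 29 (power 90.2%). The stated 29 is therefore reproduced with one value per subject, two groups and one-sided 5%. At one-sided 2.5% the normal formula gives 35; that difference is a separate matter.

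**2. Standard error of the toric mean.** Over n subjects with two eyes each, Var(mean) = SD²(1+ρ)/(2n). Treating eyes as independent drops the factor (1+ρ).

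| | ρ = 0.3 | ρ = 0.5 | ρ = 0.7 |
|---|---|---|---|
| Eye-level SE, 0.32/√58 | 0.0420 | 0.0420 | 0.0420 |
| Correct SE, 0.32 × √((1+ρ)/58) | 0.0479 | 0.0515 | 0.0548 |
| Ratio, 1/√(1+ρ) | 0.88 | 0.82 | 0.77 |
| Coverage of nominal 95%, 2Φ(1.960/√(1+ρ)) − 1 | 91.4% | 89.0% | 86.7% |

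**3. Half-width of a 95% interval.** Eyes as independent: 2.002 × 0.32/√58 = 0.084 D. Two-eye mean, 28 degrees of freedom: 2.048 × 0.32 × √((1+ρ)/58) = 0.098/0.105/0.112 D.

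**4. Non-inferiority error when the true difference equals the margin.** Error = 1 − Φ(z/k), where k is the true SE of the difference divided by the SE used.

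| Nominal level and comparator | ρ = 0.3 | ρ = 0.5 | ρ = 0.7 |
|---|---|---|---|
| 2.5%; only toric group clustered, m = 29 | 3.1% | 3.5% | 3.9% |
| 2.5%; only toric group clustered, m = 100 | 3.6% | 4.4% | 5.1% |
| 2.5%; comparator fixed or equally correlated | 4.3% | 5.5% | 6.6% |
| 5%; only toric group clustered, m = 29 | 5.8% | 6.4% | 6.9% |
| 5%; only toric group clustered, m = 100 | 6.6% | 7.6% | 8.5% |
| 5%; comparator fixed or equally correlated | 7.5% | 9.0% | 10.4% |

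For the toric-only rows, k = √{[(1+ρ)/58 + 1/m] / [1/58 + 1/m]}; for the others, k = √(1+ρ). A simulation (200,000 runs, 29 normal pairs, comparator fixed) gave 4.3/5.5/6.6% for the eye-level test and 2.5/2.5/2.4% for the two-eye-mean test at nominal 2.5%.

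**5. Effect on the conclusion, at one-sided 2.5%.** The largest observed difference that passes is 0.166 D by eye against 0.152/0.145/0.138 D by subject (comparator fixed). With an equal-sized, equally correlated comparator it is 0.132 against 0.114/0.104/0.095 D. If the true difference is zero, the two analyses disagree in 0.1/0.2/0.6% of simulated trials (comparator fixed) or 2.2/4.4/6.9% (equal comparator).

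**The case against.** The strongest reply is that the only unit stated alongside the named test is the subject, and that 29 is reproduced with one value per subject. On that reading the standard error is sound and only a convention is unstated. The eye-level reading leans on a description of a cited study and on an efficacy set defined by incisions that the protocol excludes. This stands in part: the documents do not show that eyes will be treated as independent, so the harm is conditional. But the word subjects there sizes enrolment and does not define the analysed value, and no rule says how two eyes become one value.

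Second, section 10.2 leaves room for a paired-eye method. It permits one but does not require it, and it leaves the choice until the data are in hand.

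Third, section 3 expects residual cylinder similar to that with non-toric lenses. If the true difference is near zero the conclusion seldom changes. This stands, and it limits the weight of the point.

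Fourth, section 11 enters the literature mean with its own SD, so the comparator is not fixed. The 4.3/5.5/6.6% should therefore not be read without the lower toric-only range. This also stands.

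Finally, no confidence interval is explicitly planned. The coverage figures still describe how far the standard error is off, and the t-test uses the same standard error.

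**Conclusion.** The gap is real and worth fixing, but moderate. A per-eye primary outcome, two eyes per subject and a plain two-group t-test are combined without a stated unit or any provision for fellow-eye correlation. If the 58 eyes are entered as independent, the standard error of the toric mean is 12/18/23% too small at ρ = 0.3/0.5/0.7, and a nominal 2.5% error becomes about 3.1–5.1% (toric group only) or 4.3–6.6% (comparator fixed or equally correlated). These sizes rest on assumed values of ρ and m; at ρ = 0 there is no understatement.

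A reader might infer three stronger things that the documents do not support:

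- That the plan commits to analysing eyes as independent. It does not settle the unit.
- That enrolment is too small because of pairing. The 29 counts subjects, and a two-eye-mean analysis keeps at least 90% power at one-sided 5% against an equal comparator.
- That a finding of non-inferiority would be spurious. Near a true difference of zero the two analyses nearly always agree.

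The main gain is a valid standard error for the mean that the study sets out to report.

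**What to change.** In sections 10 and 11:

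- State that the subject is the independent unit. Analyse each subject's two-eye mean residual cylinder with n = subjects, and take the non-inferiority comparison from that analysis. Pairs should be nearly complete, because section 7.4 discontinues a subject whose surgery is aborted in either eye.
- If single-eye data are to be kept, use instead an eye-level linear mixed model with a random subject effect. A fixed lens-model effect fits section 8.1, which assigns a different model to each eye.
- State the unit and the number of units behind the literature SD of 0.32 D. If it is per eye, a two-eye mean has SD 0.32 × √((1+ρ)/2) = 0.26/0.28/0.30 D, which is on a different scale. Do not pool the two SDs; use an unequal-variance (Welch) comparison.

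The cost is one or two sentences and a slightly wider interval than the eye-level one: half-width 0.098–0.112 D against 0.084 D. No extra subjects are needed at the one-sided 5% level that reproduces 29: power with the two-eye mean is 97.7/96.0/93.9% against a comparator of 29 subjects with the same structure. At one-sided 2.5% it is 95.2/92.2/88.7%, slightly below 90% only at ρ = 0.7.

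### Section 11 sizes the study for non-inferiority with a 0.25 D margin, but the primary t-test has no margin-based null or confidence-limit rule, so as written it cannot establish non-inferiority

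*Combined protocol and SAP*

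**What the plan says.** Section 11 gives the aim, "We are looking for the toric IOLs to be non-inferior", and the sizing inputs: "a power of 0.9, an alpha of 0.05, and a 0.25D non-inferiority margin", with a literature mean of 0.40 D and SD of 0.32 D. The result is 29 subjects, raised to 32 for dropout.

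The same section names the primary analysis: "The mean residual refractive cylinders will be compared using a t-test between the two groups". One group is the published blended bifocal series, known only through its summary figures, and the other is this study. The margin does not appear in the analysis sentence.

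Two blanket rules apply. Section 10.2 says "All statistical tests will be two-sided and interpreted at a 5% significance level", and section 10.3 says "Any statistical tests of hypotheses will employ a level of significance of alpha=0.05". Neither mentions non-inferiority.

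Section 3 words the cylinder hypothesis as similarity: the toric lenses "will result in a residual refractive cylinder similar to that observed in patients with non-clinically significant astigmatism treated with non-toric ReSTOR lenses". It also expects acuity and visual quality to be similar to the non-toric models, and section 8.1 plans comparison with the literature. For these outcomes section 10.2 offers only "standard descriptive statistics and other tests as deemed appropriate based on the characteristics of the data to be analyzed".

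**The concern.** A two-sided t-test of two means has zero difference as its null hypothesis unless another null is stated. A non-inferiority claim needs a different null: that the toric lens is worse by at least 0.25 D. The plan uses the margin to choose the number of subjects and then gives it no part in the conclusion.

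The primary conclusion depends on this. With about 29 subjects, failing to find a difference is weak evidence that none of importance exists, and a smaller or noisier study fails to find one more often. Because the hypothesis is worded as similarity, a non-significant p-value could easily be reported as meeting it. The study is also open-label with no concurrent control, so an unstated decision rule could be settled after the data are seen.

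**Working it through.** **Inputs.** From section 11: margin 0.25 D, SD 0.32 D, alpha 0.05 (sidedness not stated), power 0.90. From section 10.2: two-sided tests at 5%. Assumed: the toric SD is also 0.32 D, the subject is the unit of analysis, and the comparator group has 29 subjects, because the documents do not give its size. The comparator size is varied in step 4.

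**1. Reproduce the 29.** For two groups and zero true difference, n per group = 2 × [SD × (z_alpha + z_power) / margin]².
- One-sided 0.05: 2 × [0.32 × (1.645 + 1.282) / 0.25]² = 28.06, so **29**. The exact t calculation also gives 29 (power 0.902).
- One-sided 0.025: 2 × [0.32 × (1.960 + 1.282) / 0.25]² = 34.43, so 35 (36 by exact t).
- Treating the literature mean as a fixed value gives 16 (one-sided 0.05) or 20 (one-sided 0.025).

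Of these, only the two-sample, one-sided 0.05 non-inferiority calculation gives the stated 29. Dropout: 29 × 1.1 = 31.9, so 32, as stated.

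**2. What the t-test for zero difference does at 29 versus 29.**
- SE = 0.32 × √(2/29) = 0.0840 D.
- t(0.975, 56 df) = 2.003, so the CI half-width is 2.003 × 0.0840 = 0.168 D.
- The test is non-significant for any observed excess up to **0.168 D**.

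**3. What non-inferiority requires with the same data.**
- Two-sided 95% CI: observed excess below 0.25 − 0.168 = **0.082 D**.
- One-sided 95% limit: t(0.95, 56 df) = 1.673, and 0.25 − 1.673 × 0.0840 = **0.109 D**.

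For an observed excess from 0.082 D (or 0.109 D) to 0.168 D, the t-test finds no difference and non-inferiority is not shown.

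**4. Chance of a non-significant t-test if the toric lens is truly 0.25 D worse** (noncentral t, two-sided 5%).

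| Study n | Comparator n | SD (D) | P(non-significant) |
|---|---|---|---|
| 29 | 29 | 0.32 | 0.168 |
| 29 | 20 | 0.32 | 0.251 |
| 29 | 60 | 0.32 | 0.073 |
| 32 | 32 | 0.32 | 0.132 |
| 29 | 29 | 0.40 | 0.352 |
| 29 | 29 | 0.50 | 0.535 |

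A margin-based rule holds this error at 0.025 (two-sided 95% CI) or 0.05 (one-sided 95% limit) whatever the n or SD.

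**5. Power of a margin-based rule at zero true difference, equal groups.**

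| n per group | One-sided 95% limit | Two-sided 95% CI |
|---|---|---|
| 29 | 0.90 | 0.83 |
| 32 | 0.93 | 0.87 |
| 36 | – | 0.90 |

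**The case against.** The strongest reply is that a margin-shifted t-test was intended all along. Aim, margin and t-test stand in one paragraph, a t-test is a normal way to test a shifted null, and the 29 reproduces as exactly such a calculation. That may well be the intention. It is not written, however, and the one written rule on testing, two-sided at 5% throughout, conflicts with the one-sided 0.05 sizing. On this kinder reading the primary decision rule is still unstated and its level contradictory.

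It can also be said that section 6 sets a descriptive objective, a normative standard. That lowers the stakes for the description of outcomes but does not remove the non-inferiority claim that section 11 makes and powers.

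Three stronger readings are tempting, and the documents do not support them:
- **That the sponsor plans to treat p>0.05 as non-inferiority.** No section says so. The plan leaves that reading open but does not adopt it.
- **That acuity and quality of vision are assigned the same t-test.** The only t-test named is for residual cylinder. The gap for the secondary outcomes is that there is no named method and no margin.
- **That the test could declare the toric lens worse while the whole 95% CI lies inside the margin.** A significantly worse result has an upper limit above twice the half-width. At 29 versus 29 that is 2 × 0.168 = 0.336 D. With 20 comparators the half-width is 2.012 × 0.32 × √(1/29 + 1/20) = 0.187 D, giving 0.374 D; with 60 it is 1.988 × 0.32 × √(1/29 + 1/60) = 0.144 D, giving 0.288 D. All exceed 0.25 D, so this cannot occur at those sizes.

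**Conclusion.** The point holds for the primary analysis. The margin drives the sample size, but no margin-based null, confidence-limit rule or success criterion is stated. Followed as written, the two-sided t-test answers whether the means differ, which is not the question section 11 poses.

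If non-significance were taken as success, the chance of passing a lens that is truly 0.25 D worse would be about 17%, against an intended 2.5% to 5%. The figure rests on SD 0.32 D in both groups, 29 versus 29 and the subject as the unit. It is 25% with 20 comparators and 7% with 60, and rises with a larger SD.

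For the secondary similarity hypotheses the finding is narrower: the plan gives neither a method nor a margin, so it provides no basis for calling those outcomes similar. This should be settled before the data are reviewed, because the primary conclusion depends on it.

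**What to change.** **Section 11.** Replace the t-test sentence with: *Non-inferiority is concluded if the upper confidence limit for (toric mean minus literature mean), using the SD and size of both groups, is below 0.25 D. The p-value for zero difference is not used for this conclusion.* State the size of the literature group, which the limit requires.

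**Level.** State it and reconcile it with section 10.2. There are two consistent choices:
- A one-sided 95% limit (two-sided 90% CI) matches the 29 subjects and 90% power. Section 10.2 then needs an explicit exception for the primary comparison.
- A two-sided 95% CI matches section 10.2. Section 11 must then restate power as about 83% at 29 (87% at 32, equal comparator group), or plan about 36 per group for 90%.

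**Section 10.2.** Report acuity and quality of vision as differences from the literature with 95% CIs. Make no similarity claim unless the interval lies within a margin fixed before data review.

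**Cost.** A few sentences and no new measurements. The non-inferiority and similarity claims become harder to make, and a two-sided 95% CI also means a lower stated power or more subjects.
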